1. STUDY SUMMARY

Provide a brief summary of the proposed research (in language that can be understood by a non-scientist).

Response:

We propose a prospective observational cohort study in order to investigate the perioperative respiratory complications of deep extubation in adults undergoing head and neck surgery at Massachusetts Eye and Ear. Data pertaining to perioperative respiratory complications from adult patients presenting to MEE for head and neck surgery who undergo deep extubation will be collected for this study.

2. SPECIFIC AIMS

List the specific aim(s) and objective (s) of the study (i.e., what does the study hope to accomplish). Include any secondary and exploratory aims and objectives (e.g., biomarkers, genetic analyses).

Response: To assess the perioperative respiratory complications rate of deep extubation in adult patients undergoing head and neck surgery at MEE.

3. BACKGROUND AND SIGNIFICANCE

Describe the scientific background and rationale for the study.

- Provide a critical review of the relevant literature and the state of current knowledge on the topic. Discuss deficiencies or gaps in knowledge that make the study worth doing. Include a list of literature cited in an appendix at the end of this protocol.
- Discuss the importance of the topic with respect to scientific knowledge, clinical practice, public health, impact on individuals/community, incidence, prevalence, mortality and morbidity, as applicable.

Response:

Tracheal extubation in patients undergoing head and neck surgery may be followed by several respiratory complications, such as coughing, desaturation, laryngospasm, bronchospasm, and airway obstructions.^{1,2} The trachea can be extubated when the patient is still deeply anaesthetized or after he/she fully regains consciousness. Currently, the default method of extubation at Massachusetts Eye and Ear Infirmary (MEEI) is deep extubation. In contrast, the default method of extubation in most centers in the United States is awake extubation.

Respiratory complications may occur following both deep and awake extubation, and the superiority of one method over another has not been established. When the trachea is extubated in light stages of anesthesia or after the patient has regained consciousness, there can be significant increases in heart rate and arterial pressure that may continue into the recovery period. This increase in blood pressure and heart rate may be partially due to straining during extubation. In patients in whom these stimulatory effects can be detrimental, tracheal extubation under deep anesthesia may reduce the incidence and degree of these complications; however, tracheal extubation under deep anesthesia may cause respiratory complications, including laryngospasm, bronchospasm, and negative pressure pulmonary edema.³

There is a paucity of research related to deep or awake extubation in adults. Specifically, such studies are lacking in patients who undergo head and neck surgery. In a prospective survey of respiratory complications of tracheal intubation and extubation of 1005 patients 16 years or older who underwent elective general anesthesia, Asai et al found that the incidence of respiratory complications was higher in the deep versus the awake extubation group, regardless of the type of operation.³

However, studies in the pediatric population have shown a different picture. In children undergoing adenotonsillectomy, von Ungern-Sternberg et al have shown that patients who were extubated while awake had a higher incidence of severe coughing and desaturation at emergence, as well as a higher rate of hoarse voice on the first postoperative day.⁴ Although there was no difference in the instances of oxygen desaturation between the two methods of extubation, these episodes tended to be more common and of longer duration in the awake group. In contrast, the children who were extubated while deeply anaesthetized showed an overall higher incidence of partial airway obstruction.

Given the serious nature of untoward respiratory events in the perioperative period associated with tracheal extubation, we propose a prospective observational cohort study to further assess the perioperative respiratory complications of deep extubation, the default method of extubation at MEE in adults undergoing head and neck surgery.

References:

4. STUDY DESIGN

Provide a detailed description of the study design (e.g. cross-sectional, stratified, longitudinal, prospective cohort, case-control, randomized, placebo-controlled, masked/double masked, feasibility, pilot, proof-of-concept, etc.).

Explain why this study design is appropriate for this study.

Response:

Our study is a prospective observational cohort study. We will record the respiratory complications, such as bronchospasm, laryngospasm, respiratory depression, desaturation, persistent cough, and apnea after deep extubation in patients undergoing head and neck surgery at MEE.

We will also collect following data:

- 1) Length of time from the end of surgery to leaving the OR;
- 2) Length of stay from admission to the PACU to discharge home;
- 3) Any unplanned hospital admission due to perioperative respiratory adverse events.

5. SUBJECT INFORMATION

- a) Target Enrollment- Specify the number of subjects you plan to enroll and justify why this number is sufficient to achieve adequate power for statistical analysis taking into account anticipated screen failures and drop-outs. Include sample size by cohort if the study has multiple cohorts.

Response: Our proposed sample size of 300 patients will enable us to report the complication rates with adequate precision in terms of a sufficiently narrow two-sided 95% confidence interval. For example, if the observed respiratory complication rate is 30%, as was reported by Asai T et al (1), our confidence interval will have a half-width of 5%. If a complication rate that we observe is 35%, the half-width of our confidence interval will be 6% (nQuery Advisor version 7). We have used nQuery Advisor version 7 for the calculation of our sample size. For a CI of 95%, $\alpha = 0.05$, $P = 80\%$, and a complication rate of deep extubation of 30%, as reported by Asai T et al (Asai T, Koga K, Vaughan RS, et al. Respiratory complications associated with tracheal intubation and extubation. *Br. J. Anesth.* 1998, 80, 767–775.), we will require a sample size of 300.

- b) If this is a multi-center study and other sites rely on the MEE HSC as the IRB of record, please specify the total number of subjects required by all sites to achieve sufficient power.

Response: N/A

- c) Provide justification that the researchers have access to sufficient numbers of eligible subjects to meet target enrollment goals (e.g., researcher’s own patients, clinic patients with a specific diagnosis, subjects from previous studies who agree to participate in future studies).

Response: Potentially eligible subjects for this study are all adult patients who undergo head and neck surgery as well as deep extubation at the end of the surgery per the discretion of the anesthesiologist assigned to the case. Deep extubation is the default extubation method practiced at MEE. Therefore, there will be a sufficient number of potentially eligible subjects to meet the target enrollment goals.

6. ELIGIBILITY CRITERIA

- a) Inclusion Criteria - Inclusion criteria are the specific characteristics of the study population(s) required for study enrollment (e.g., ages, gender, condition or disease.) List the inclusion criteria in a bulleted list.

Response: Adult men and women who present to MEE for head and neck surgery and undergo deep extubation will be included.

- b) Exclusion Criteria - Provide specific criteria for determining ineligibility to participate. Provide justification for their exclusion (e.g., pregnant women).

Note: Exclusion criteria are not always clinical in nature. Exclusion may also include circumstances that interfere with:

- the participant’s ability to give informed consent (diminished cognitive capacity or a language other than English and an interpreter unavailable)
- contraindications to the study treatment(s)/procedure(s)
- taking certain concomitant medication(s) or
- conditions that interfere with a patient's ability to comply with all study procedure(s)

Response: We do not exclude anyone from the study.

NOTE: Per federal regulations, the risks and benefits of research must be fairly distributed among the populations that could benefit from the research. No groups of persons (e.g., gender, pregnant women, children, minorities, non-English speakers) should be categorically excluded from research without a valid scientific or ethical reason to exclude such groups.

- c) Describe your rationale that the study population is representative of populations that may potentially benefit from the research, or the rationale for excluding certain groups, if applicable.

Response: N/A

7. RECRUITMENT PROCESS

NOTE: HIPAA does not permit non-MEE physicians to disclose patient information to Mass Eye and Ear for research recruitment. Non-MEE physicians may inform their patients of a research study and allow the patients to self-disclose their interest to the MEE study team.

Provide a detailed description of the recruitment plan (consistent with information you provide in the PRA), who is responsible for recruitment, how and when subjects will be recruited (i.e., flyers, advertisements, letters and oral/telephone scripts, email, at clinic appointments, etc.). Note: The HSC must review all recruitment materials. Please upload these materials into IRBNet with this submission.

Response: All adult patients who undergo head and neck surgery as well as deep extubation at the end of the surgery will be eligible for this study. The protected health information, including only names, MRN, and Date of surgeries of all eligible patients will be accessed from Epic at the screening process. We will not use email, fliers or brochures to recruit subjects. All surgeons performing head and neck surgery and all anesthesiologists at MEE will be notified of and informed about the study. Upon arrival to the preoperative area at MEE two hours prior to surgery, patients will be registered and seen by the preoperative nurse. Afterwards, an anesthesiologist will perform the preoperative evaluation. A data-recording form will be handed to the anesthesiologist in order to collect all the information requested in the form for patients undergoing deep extubation at the end of the surgery. The investigator and study coordinator will monitor the data collecting.

8. CONSENT PROCESS

- a) 8a. Describe the consent process in detail. Include the following information:
- who (e.g., physician, nurse, coordinator) will obtain consent,
 - their knowledge/experience in obtaining consent
 - location of the consent process
 - use of the Documentation of Consent Process Form
 - how the study information is presented (written consent form, orally, study information sheet, use of “short form” or translated consent etc.)
 - timing of consent (e.g., during pre-surgical visit, about one week before the screening visit)

Response: We request a waiver of informed consent from the HSC.

- b) 8b. How will you assess a subject’s understanding of the research initially and over the course of the study? Is the presentation of study information appropriate for the study population (low vision, hearing impaired)? Describe specific provisions for subjects with limited understanding (e.g., a family member or other appropriate 3rd party is involved in the consent process).

Response: N/A

- c) 8c. If the research-related intervention or interaction will occur on the same day that the subject initially receives information about the study, justify why this is appropriate/necessary.

Response: N/A

- d) 8d. Describe provisions in place for non-English speaking subjects (view guidance on the HRPP Sharepoint Site <http://sharepoint/departments/research/HumanResearch/SitePages/Home.aspx>), including use of translators during the consent process and the translation of consent documents.

Response: N/A

- e) 8e. If a subject cannot read the consent form (e.g., low literacy, low or no vision) or cannot hear the person obtaining consent, explain how you will conduct the consent process and the provisions to accommodate subjects with limited or no hearing and/or limited or no vision.

Response: N/A

9. STUDY PROCEDURES

- a) Provide a detailed description of all study procedures and intervention(s) each subject and/or cohort will experience. Provide a schedule of visits and the procedures that occur at each visit (e.g., tests, questionnaires, surveys, imaging or other interventions.). If the study also involves standard of care, differentiate between research only procedures and standard of care.

Response:

Preoperative Phase	
 • Research only: All surgeons who perform head and neck surgery at MEE will be notified of and informed about the study. • Upon arrival to the preoperative area at MEE two hours prior to surgery, patients will be registered and then seen by the preoperative nurse. • Next, an anesthesiologist will perform the preoperative evaluation. • Women aged 18 years and older will be offered a pregnancy test screening. • An IV catheter will be placed in all patients in the preoperative holding area on the surgical floor. • Research only: A data-recording form will be handed to the anesthesiologist. • Research only: The anesthesiologist will fill out data sheet questions related to patient’s past medical history from the anesthesia preoperative evaluation form. • Research only: The data-recording form will include multiple parameters that will be recorded in the perioperative period to quantify any adverse respiratory events including: 
 1. Oxygen saturation at the following intervals: 5 minutes prior to extubation; immediately before extubation; every minute for the first 10 minutes following extubation, except during transport to the PACU; and subsequently, every 5 minutes for the ensuing 30 minutes; 2. Endtidal CO₂ at the time of extubation; 3. Desaturation to less than 95% for more than 10 seconds; 4. Type and amount of opiates administered during the surgery; 5. Time from the end of the surgery to leaving the OR;
--------------------	---

	
 6. Systolic and diastolic blood pressure and heart rate at the time of extubation, as well as upon arrival in the PACU, and subsequently, every 5 minutes for the first 30 minutes; 7. Episodes of persistent cough, defined as 3 or more consecutive coughs; 8. Episodes of complete or partial laryngospasm; 9. Episodes of bronchospasm; 10. Incidence of negative pressure pulmonary edema; 11. Incidence of vomiting; 12. Incidence and type of airway interventions; 13. Episodes of apnea; 14. Type and amount of opiates administered during the PACU stay; 15. Length of stay in minutes from admission to the PACU to discharge home; 16. Any unplanned hospital admissions due to perioperative respiratory adverse events;

Intraoperative Phase
	
 • Standard ASA monitors, including pulse-oximetry, ECG, non-invasive blood pressure, thermometer, and capnography, will be applied in all patients. • All patients will be preoxygenated prior to induction. • Induction: 
 ○ The choice of induction drugs will be at the discretion of the anesthesiologist. • Maintenance: 
 ○ The choice of maintenance drugs, including choice and dose of opiates, will be at the discretion of the anesthesiologist. • Emergence and extubation: 
 ○ The choice extubation method (deep vs awake) will be at the discretion of the anesthesiologist.

	
 ○ Deep extubation criteria will be at the discretion of the anesthesiologist. ○ An oral or nasal airway will be placed in patients immediately after deep extubation.
Postoperative Phase	
 ● All patients will be transported to the post-anesthesia care unit (PACU) with a facemask receiving oxygen. ● The anesthesiologist will remain with the patient until he/she is stable enough to be handed off to the PACU nurse. ● Patients will be continued on supplemental oxygen until fully awake; they will be placed on room air when able to maintain adequate oxygen saturation as assessed by the PACU nurse. ● Research only: The data-recording form will be handed to data recorder in the PACU to be completed.
Discharge	Patients will be discharged home or to the floor after meeting PACU discharge criteria.
Analysis	Research only: The data will be analyzed and reported.

b) 9b. Describe any data and/or sample banking, if applicable.

Response: N/A

c) 9c. If the study includes randomization describe the randomization process and randomization ratio, (include block size, permutations and stratification, if applicable.).

Response: N/A

d) If there are circumstances under which the researcher may withdraw participants, describe the conditions and process for withdrawal. Describe how subjects can withdraw from the study (e.g., calling or emailing the investigator/study coordinator).

Response: N/A

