10. STUDY OUTCOMES

- a) **Primary Outcome Measure(s)** - describe how you will measure the primary and other outcomes of the study (e.g., blood pressure change, changes in visual acuity using a specific test, pain scales, responses on a questionnaire, etc.). Upload copies of your data collection tools and/or a list of all variables/data points you will collect.

Note: Primary outcome measures may be measured in various ways such as:

- binary (e.g. improvement in symptoms vs. no improvement in symptoms)
- continuous (e.g. weight - kg, blood loss - mL)
- ordinal (e.g. pain - mild, moderate, severe)
- time to event (e.g. survival)
- counts (e.g. number of infections, number of events occurring)

Response:

Primary outcome measures include:

- 1) **Desaturation to less than 95% for more than 10 seconds;**
- 2) **Episodes of persistent cough, defined as 3 or more consecutive coughs;**
- 3) **Episodes of complete or partial laryngospasm;**
- 4) **Episodes of bronchospasm;**
- 5) **Incidence of negative pressure pulmonary edema;**
- 6) **Obstruction that requires maneuvers, oral airway or jaw thrust**

- b) Describe any secondary or other outcomes (exploratory):

Secondary outcome measures include:

- 1) **Length of time from end of surgery to leaving the operating room;**
- 2) **Length of stay from admission to and discharge from the PACU Stage 1 and 2;**
- 3) **Incidence of unexpected hospital stay related to perioperative respiratory complications.**
- 4) **Incidence of sore throat**

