13. RISKS AND DISCOMFORTS AND MINIMIZATION OF RISKS

Risk is the probability and magnitude of harm or discomfort anticipated as a result of participation in the research.

Minimal risk means the probability and magnitude of harm or discomfort anticipated in the research are not greater in and of themselves than those ordinarily encountered in daily life or during the performance of routine physical or psychological examinations or tests.

- a) Describe any risks of harm to subjects and/or anticipated discomfort(s) that are reasonably foreseeable, even if unlikely. Identify the safeguards you will put in place to minimize the occurrence of these risks and discomforts. Risks of harm and discomfort may include: physical harm/discomfort, psychological harm/discomfort, legal harm/discomfort, social harm/discomfort and economic harm.

Response: There are two methods of extubation in patients undergoing anesthesia: deep or awake. Currently, deep extubation is the default extubation method at MEE. However, in almost every other institution in the country, awake extubation is the default method. Risks of airway complications are associated with both methods and can include the following: 1) desaturation and hypoxia; 2) partial or complete laryngospasm; 3) bronchospasm; and 4) negative pressure pulmonary edema. Since this study is observational, there will be no risk for patients accruing from participating in the study. Recording of additional data by the anesthesiologist assigned to the case after extubation will not impact clinical care of the patient as the anesthesiologist will be monitoring the same vital signs whether the patient is part of the study or not. The computerized anesthesia manager program captures all the vital signs until the patient is disconnected and transported to the PACU. In the PACU, the data

recorder will be recording the additional data. The only document with the patient’s identifiers will be the data sheet, which will be filled out by the anesthesiologist during the case and by the data recorder in the PACU. Subsequently, all data will be recorded as a research record on an MEE password protected computer. Patient’s data sheets will be locked in the drawers located in the anesthesia office on the 7th floor of the MEE main building. Only the study coordinator and the principal investigator have access to these drawers. Consequently, the patients’ data will remain confidential all the time.

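### The plan describes no recorded saturation during transport to the PACU, so the primary desaturation rate may be biased low by an unknown amount

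*Combined protocol and SAP*

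**What the plan says.** The first-listed primary outcome in Section 10(a) is "Desaturation to less than 95% for more than 10 seconds". It has no stated observation window, no named data source and no exception for transport. The same event is item 3 of the data-recording form in Section 9(a), again without an exception.

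The scheduled readings are a separate item. Item 1 of the form asks for saturation "every minute for the first 10 minutes following extubation, except during transport to the PACU", "and subsequently, every 5 minutes for the ensuing 30 minutes". Item 6 ties blood pressure and heart rate to arrival in the PACU; item 1 ties no saturation reading to arrival.

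On the automated record, Section 13(a) says the anesthesia program "captures all the vital signs until the patient is disconnected and transported to the PACU", and that in the PACU the data "recorder will be recording the additional data". Section 19(a) repeats both statements.

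On care during the interval, the postoperative part of Section 9(a) says: "All patients will be transported to the post-anesthesia care unit (PACU) with a facemask receiving oxygen". It adds: "The anesthesiologist will remain with the patient until he/she is stable enough to be handed off to the PACU nurse".

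Section 12 contains only the sample-size paragraph. It gives no rule for deriving the outcome or for handling time in which saturation was not observed.

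**The concern.** The outcome covers more time than the recording plan does. The exception for transport is written into the most intensive stretch of observation, the first 10 minutes after deep extubation, so the authors evidently expected transport to fall there. The automated record ends at about the same moment. This is a stated exclusion, not just silence.

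The aim in Section 2 is the complication rate itself, and there is no control group in which the same gap could cancel. An event that is missed can only lower the rate. Enrolling more patients would not help, because the interval would narrow around the same shifted value. The times needed to measure the gap also cannot be relied on later if they are not written down at the time.

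**Working it through.** **1. The plan's own precision figures.** Sections 5(a) and 12 give n = 300, a two-sided 95% interval, and half-widths of 5% at a rate of 30% and 6% at 35%.

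- Wald: 1.96 × √(0.30 × 0.70 / 300) = 5.19 points; 1.96 × √(0.35 × 0.65 / 300) = 5.40 points.
- Clopper-Pearson (half the interval's length): 5.33 and 5.54 points.

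The exact method rounds to the stated 5% and 6%, so the figures reproduce to whole percents and are not in dispute. The 30% is a rate for any respiratory complication, not for desaturation.

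**2. Which recording covers which interval.**

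| Interval | Item 1 readings | Automated record | Item 3 (the outcome) |
|---|---|---|---|
| OR, after extubation | every minute | yes | yes |
| Transport, within 10 minutes of extubation | excepted | ended | not excepted, but no source described |
| PACU | every minute to minute 10, then every 5 minutes | no; data recorder | yes |

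One-minute spot readings could not by themselves establish an event lasting more than 10 seconds. Item 3 must therefore rest on some other observation, which the plan does not describe for any interval. In transport, neither scheduled readings nor an automated trace is available to support it.

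**3. Who could be misclassified.** Only patients whose sole qualifying event begins and ends in transport. A patient who also desaturates in the OR or PACU, or who stays below 95% for more than 10 seconds after arrival, can still be counted.

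**4. Size.** Let p be the true desaturation rate and s the share of event patients whose only event was in transport and went unrecorded. If these patients are treated as event-free:

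observed rate = p × (1 − s); bias = −p × s.

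The documents give neither a desaturation rate, nor s, nor a transport time. Both p = 15% and the range of s are assumptions.

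| s | Observed rate, p = 15% | Bias (points) |
|---|---|---|
| 0 | 15.00% | 0 |
| 5% | 14.25% | −0.75 |
| 10% | 13.50% | −1.50 |
| 20% | 12.00% | −3.00 |
| 30% | 10.50% | −4.50 |

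The matching half-width is 1.96 × √(0.15 × 0.85 / 300) = 4.04 points. Bias reaches it at s = 4.04 / 15 = 27%.

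At p = 30%, the plan's any-complication rate used only as a second illustration, s of 5% to 30% gives 28.5% to 21.0%. Bias reaches the half-width at s = 5.19 / 30 = 17%.

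A bias smaller than the half-width is not harmless. At p = 30% and s = 10% the bias is 3 points, and the nominal 95% Wald interval covers the true rate about 76% of the time (exact binomial sum at n = 300).

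**The case against.** The strongest reply is that the exception belongs only to the scheduled readings in item 1. The outcome has its own field, item 3, with no exception. The anesthesiologist stays with the patient until handoff in the PACU, and the form then passes to the data recorder, so a transport event could be written down by hand. Section 13(a) says the computer program stops capturing; it does not say oximetry stops. Every patient is on facemask oxygen, and the number lost may be negligible. This is also one of six listed primary outcomes.

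Most of that stands, and it makes the bias conditional. It does not close the gap. A numeric threshold held for more than 10 seconds needs an oximeter reading, and the plan names none between disconnection and the PACU. If one is worn, the plan should say so and record it.

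A further reply is that readings resume on arrival anyway. That holds if the patient arrives within 10 minutes of extubation. After minute 10 the readings are five minutes apart, so a saturation on arrival is not guaranteed.

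Three stronger readings are tempting, and the documents do not support them:

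- A reader might infer that the plan counts transport events as non-events. No section says so. There is no coding rule, and the interval could equally be treated as missing.
- A reader might set a bias of 3 to 9 points at p = 30% (s of 10% to 30%) against the stated 5-point half-width. That 30% is not a desaturation rate, and a range of s that starts above zero leaves out the case of no bias.
- A reader might conclude that the rate is not comparable with that of centres monitoring continuously. The documents describe no other centre's transport monitoring.

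**Conclusion.** The point holds in conditional form. The plan exempts transport from the scheduled saturation readings and ends automated capture at disconnection. It describes no recorded source for that interval and gives no rule for it, while the primary outcome has no matching exception.

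The direction is certain if events are missed: the rate is too low. The size is unknown. It is zero if no patient's only event falls in transport. Under the assumed true rate of 15%, it is 0.75 to 4.5 points for 5% to 30% of event patients missed, against a half-width of about 4 points. These figures rest on three assumptions: the rate, the share missed, and that missed patients are treated as event-free.

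The plan should be changed, because the remedy is cheap and works only if it is in place while patients are being enrolled.

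**What to change.** 1. Add three fields to the existing form: time of OR monitor disconnection, time of PACU monitor connection, and first SpO₂ on PACU arrival.
2. If an oximeter is already worn in transport, record its lowest reading, and enter under item 3 any spell below 95% lasting more than 10 seconds.
3. Leave the primary definition as it is. State its observation window and data source, and label the primary rate as covering monitored OR and PACU time unless transport readings were recorded.
4. Report the median unmonitored time.
5. Add a sensitivity analysis that also counts patients with an arrival SpO₂ below 95% as possible transport desaturations. This must stay a sensitivity definition. One spot reading does not meet the duration criterion, may be transient or an artefact, and still misses events that resolved on the way.

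The cost is three form fields, one extra line in the results and a slightly narrower claim. No new monitoring and no change in care are involved.

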- e) Will samples from MEE be provided to outside sources? Please specify to whom you will provide MEE samples and what information/data will accompany each sample. Please note that that a Material Transfer Agreement will be required for this research activity.

Response: No

19. DATA and SAFETY MONITORING PLAN (DSMP)

- a) If the research is no more than minimal risk, describe any provisions in place to ensure the safety of participants. In minimal risk studies, there is always the risk of loss of confidentiality and privacy. However, minimal risk studies involving blood draws, imaging, and eye exams may have risks associated with the study procedure.

Response: Risks of airway complications are associated with both awake and deep extubation methods and can include the following: 1) desaturation and hypoxia; 2) partial or complete laryngospasm; 3) bronchospasm; and 4) negative pressure pulmonary edema. Since this study is observational, there will be no risk for patients accruing from participating in the study. Recording of additional data by the anesthesiologist assigned to the case after extubation will not impact clinical care of the patient as the anesthesiologist will be monitoring the same vital signs whether the patient is part of the study or not. The computerized anesthesia manager program captures all the vital signs until the patient is disconnected and transported to the PACU. In the PACU, the data recorder will be recording the additional data. The only document with the patient's identifiers will be the data sheet, which will be filled out by the anesthesiologist during the case and by the data recorder in the PACU. Subsequently, all data will be recorded as a research record on an MEE password protected computer. Patient's data sheets will be locked in the drawers located in the anesthesia office on the 7th floor of the MEEI main building. Only the study coordinator and the principal investigator have access to these drawers. Consequently, the patients' data will remain confidential all the time.

- b) If the research is more than minimal risk, please provide a detailed data and safety monitoring plan (DSMP). Include the individual(s) or group responsible for data and safety monitoring (e.g., PI, specific members of the study team, independent monitor(s), a convened Data and Safety Monitoring Board - DSMB) Please see the guidance document in IRBNet for developing a DSMP.

Response: N/A

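### Length of stay (secondary outcome 2) ends at PACU discharge in Sections 10 and 11 but at discharge home in Section 4 and form item 15, so the listed item misses the outcome for patients sent to the floor

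*Combined protocol and SAP*

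**What the plan says.** The combined protocol and SAP describes this interval in four main places.

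- Section 10b, secondary outcome 2: "Length of stay from admission to and discharge from the PACU Stage 1 and 2". Section 11b, item 2, repeats it. A question later in 11b refers to discharge from the PACU without naming a stage, which is compatible.
- Section 4, item 2 of the further data to be collected: "Length of stay from admission to the PACU to discharge home".
- Section 9, data-recording form item 15: "Length of stay in minutes from admission to the PACU to discharge home".

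Three other statements bear on who is affected.

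- Section 9, Discharge row: "Patients will be discharged home or to the floor after meeting PACU discharge criteria".
- Section 6b, on exclusions: "We do not exclude anyone from the study".
- Section 9, form item 16, captures "Any unplanned hospital admissions due to perioperative respiratory adverse events".

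On data capture, Section 19a says: "In the PACU, the data recorder will be recording the additional data". Section 12 contains only the sample-size paragraph. It gives no analysis of length of stay and no rule for patients who do not go home.

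**The concern.** The outcome and the item meant to capture it stop the clock at different events. For a day-surgery patient this may make no difference. For a patient who leaves the PACU for a ward bed, PACU discharge and discharge home are separate events, and the item asks for the one the outcome does not use.

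At stake is whether secondary outcome 2 can be reported for the whole cohort. If item 15 is left blank for floor patients, the reported stay describes only those who went home. The missing values would not be a random subset, because they would include patients admitted for the respiratory complications that the study sets out to describe. Section 11b also asks a question about PACU length of stay, and it would be answered on the same incomplete data.

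**Working it through.** The plan gives no figure for this outcome, so there is nothing to reproduce. The check is a comparison of the definitions by patient route.

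**End point by section**

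| Place | Clock starts | Clock stops |
|---|---|---|
| Section 10b, outcome 2 | PACU admission | Discharge from PACU Stages 1 and 2 |
| Section 11b, item 2 | PACU admission | Discharge from PACU Stages 1 and 2 |
| Section 4, item 2 | PACU admission | Discharge home |
| Section 9, form item 15 | PACU admission | Discharge home |

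**Consequence by route out of the PACU**

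| Route | Sections 10 and 11 | Section 4 and item 15 |
|---|---|---|
| Home directly from Stage 2 | Defined | Defined; can be the same time |
| Planned floor stay | Defined; ends at PACU discharge | Not available in the PACU: blank, or includes ward time |
| Unplanned admission | Defined; ends at PACU discharge | Same problem |

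**Are the second and third routes in the cohort?** Yes. The Discharge row in Section 9 names the floor as a destination, and Section 6 excludes no one, so patients with a planned floor stay are eligible. Form item 16 and secondary outcome 3 anticipate unplanned respiratory admissions.

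**Does another listed item supply the missing time?** No. Item 14 ("Type and amount of opiates administered during the PACU stay") presupposes a PACU stay with an end but does not ask for its time. Item 16 identifies unplanned respiratory admissions only, so planned floor patients cannot be recognised from the listed items.

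**Does another source supply it?** The plan does not say so. Section 20c says that Epic stores patient information. Section 7 describes Epic access at screening for names, record numbers and surgery dates. Neither names Epic as the source of PACU times.

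**Scale.** The number of patients affected is 300 × f, where f is the share sent to the floor. Only the 300 comes from the plan. Purely as an illustration, with assumed values of f:

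- f = 5%: 300 × 0.05 = 15 affected, 285 remaining
- f = 20%: 300 × 0.20 = 60 affected, 240 remaining
- f = 40%: 300 × 0.40 = 120 affected, 180 remaining

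These figures show how the problem scales. They do not estimate its size.

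**The case against.** The strongest reply is that the outcome itself is stated consistently. Sections 10 and 11 agree, and the other two places are a data list and a form line, neither labelled as secondary outcome 2. Item 15 is in minutes, starts at PACU admission and is completed by a recorder in the PACU. The Discharge row places departure for home or for the floor at the same moment, when PACU criteria are met. A sensible recorder might simply enter the PACU exit time for everyone. The form is not shown, and Section 9 introduces its list as parameters that the form will include, so the list may not be exhaustive. Epic may also hold PACU times. Finally, Section 10b groups secondary outcomes with exploratory ones.

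Much of this stands, and it limits what can be claimed. Three stronger inferences are not supported.

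- **Ward hours will inflate the reported stay.** The wording permits this, but no section describes follow-up on the floor. With a PACU-based recorder, a blank or a PACU exit time is more likely.
- **Analysts would reach different results from the same data.** If item 15 is the only stay variable, they inherit the same recorded values. The ambiguity arises mainly when the form is filled in.
- **The PACU discharge time will not be captured at all.** Its absence from the list in Section 9 does not prove its absence from the form or from Epic.

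The mismatch itself survives. A recorder who enters PACU exit time for a floor patient is departing from item 15 as written, and a recorder who follows it cannot supply the outcome. An unseen extra field would not settle which written definition governs.

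**Conclusion.** The point holds as an internal inconsistency that affects the measurement of one secondary outcome. For patients sent to the floor, form item 15 and Section 4 item 2 as written do not measure the stay defined in Sections 10 and 11. For patients going home from Stage 2 the two may be identical.

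The size of the effect is unknown, because the documents give neither the share of floor patients nor their length of stay. The direction of any bias from blank values cannot be determined either. The conclusion rests on reading the item literally and on the absence of any stated rule or source for floor patients.

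A reader might infer that the main results are compromised. They are not: the six primary outcomes do not use this interval, and the sample size of 300 is justified by the precision of a complication rate. The change is still worth making before data collection, because it is nearly free then and exit times may be harder to reconstruct later.

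**What to change.** 1. Reword Section 4 item 2 and form item 15 to match Sections 10 and 11: time from PACU admission to discharge from PACU Stages 1 and 2, whether the patient then goes home or to the floor.
2. Record that PACU discharge time for every patient, and state whether it comes from the form or from Epic. If from Epic, add this to the plan's description of what is accessed there.
3. Record the destination, so that floor patients can be identified and length of stay can be described by route.

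A separate time for the end of Stage 1 is optional, because the outcome can be read as one combined stay.

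The cost is one or two fields on a form that the PACU data recorder already completes, plus matching wording. Clinical care, the primary outcomes and the sample size do not change.
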